2. OBJECTIVES AND PURPOSES

2.1. Context, objectives and justification of the study

Atrial fibrillation (AF) is a heart rhythm disorder caused by abnormal electrical signals from the atria and is characterized by ineffective atrial contraction and irregular heartbeats. AF can occur in three forms: paroxysmal (episodes lasting less than 7 days), persistent or permanent (lasting more than 7 days) and irreversible (1).

Among patients with AF, more than one-third have associated valve disease, characterized by mitral stenosis or valve prosthesis (1). In this case, AF is called "valvular" (2). Conversely, in patients without associated valvular pathology, AF is said to be "non-valvular".

In France, two-thirds of AF patients are 75 years of age and older. The prevalence of AF is about 1% of the general population and increases with age to reach 10% of the population aged 80 years and over. The male/female sex ratio of prevalent cases is 3:2 (3). The absolute number of cases is equivalent between men and women because of the higher life expectancy in women (4).

Several pathophysiological mechanisms, including blood flow stasis, prothrombotic state, and hypercoagulability induced by AF, can lead to stroke (5). Clinical signs may include shortness of breath at rest, fatigue, palpitations, or chest pain. AF accounts for approximately 15% of all strokes (6).

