- For cross-sectional analyses (objectives 2, 4, 5 and 6) and analysis for exploratory objective (objective 8):
 - Inclusion of patients with:
 - An AF newly diagnosed during inclusion period.

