Number of occurrences	
Continuous variable
 
Equals to the number of occurrences where the two criteria are met:
 
 – The variable of the specified event of interest (Stroke, Major bleeding or Death) equals “Yes” – The value of the variable Date of occurrence falls in the specific OAC treatment sequence period for exposed patient and during unexposed sequence period for unexposed patient 
In

And finally, the following variables in [Table X](#) will be derived for all patients selected in the study population.

Table X. Derived variables for study population

Variable	Definition
Incident AF patient	
Binary variable (Yes / No)
 
Equals to “Yes” if:
 
 – The patient is newly diagnosed AF during the inclusion period (i.e. no AF diagnostic during the historical period) 
AND
 
 – No reported events of interest (stroke, major bleeding, and death) between the inclusion date and the first date of OAC delivery among AF patients with at least one dispensation of OAC identified within 30 days from inclusion date (cf. 9.2.3.1. Inclusion Criteria) 
Equals to “No” in other cases
 
Sensitivity analyses on incidence rate of stroke, major bleeding and death, and comparison of these events in regression analyzes will be performed on all newly diagnosed AF during the inclusion period (i.e. no exclusion of patients with reported events of interest between inclusion date and index date among those with at least one dispensation of OAC identified within 30 days from inclusion date).

Gender	
Binary variable (Female / Male)
 
See Table IIIError! Reference source not found.

Age	
Categorical variable (<65 years old / 65-74 / 75-79 / ≥80 years old)
 
See Table III

Death	
Binary variable (Yes / No)
 
See Table III

Lost to follow-up	
Binary variable (Yes / No)
 
Equal to “Yes” if the patient has no consumption or reimbursement of care in the 12 months following the date of last consumption
 
Equals to “No” in other cases

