9.4.3.2 Comparison of the incidence of stroke, major bleeding, death

The incidence rate ratio for each event of interest (stroke, major bleeding and death; see [Table VIII](#) for derivation of events of interest) will be compared using a Cox regression model with OAC exposure (see [Table VII](#) for derivation of exposure sequences) considered as time-dependent variable adjusted for covariates. Covariates will be derived at index date as indicated in [Table XV](#).

Table XV. Derived variables for confounders

Variable	Definition
Age	Categorical variable (<80 years old / 80–90 / >90 years old) See Table III
Sex	Binary variable (Female / Male) See Table III
Prescriber's specialty at initiation of OAC	Categorical variable (Hospital-based physician/ City cardiologist/ Generalist practitioners/Other) See Table III
Having Malnutrition	Binary variable (Yes / No) See Table III
Risk of falls	Binary variable (Yes / No) See Table III
Frail patients	Binary variable (Yes / No) See Table V
Morbid obesity	Binary variable (Yes / No) See Table VI
At least one visit to a nursing home	Binary variable (Yes / No) See Table VI
Concomitant treatments	Binary variable (Yes / No) for each concomitant treatment listed in Table XIV

For example, for antiplatelet drugs, equals to “Yes” if the patient has at least one reimbursement for an antiplatelet drug in the 4 months before the index date
	
HAS-BLED score	Categorical variable (0, 1, 2, 3, ≥ 4) See Table VI
CHAD₂DS₂VASC score	Categorical variable (0, 1, 2, 3, 4, ≥ 5) See Table VI
Age adjusted Charlson Cormordity Index (ACCI) adapted to SNDS data	Categorical variable (0, 1-2, 3-4, ≥ 5) See Table VI XII

9.4.3.3 *Estimation of the AF annual standardized incidence rate and prevalence*

All the variables in [Table XVI](#) will be derived for all AF patients in France in 2016, 2017, 2018 and 2019.

Table XVI. Derived variables for incidence and prevalence

Variable	Definition
Incident AF patient	Binary variable (Yes / No) See Table X
Prevalent AF patient	Binary variable (Yes / No) Equals to “Yes” if the patient is diagnosed AF during the historical period Patients belonging to the study population

9.4.3.4 *To describe the use of oral anticoagulants (OACs) in AF patients initiating treatment (AF patients exposed to OAC therapy)*

Table XVII. Derived variables for OAC treatment pattern

Variable	Definition

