Subgroups	Elderly patients (\geq 80 years old) Patients with CAD Frail patients Patients having an active cancer Patients reported with previous stroke		-Patients with high thromboembolic risk	Elderly patients (\geq 80 years old) Patients with CAD Frail patients Patients having an active cancer Patients reported with previous stroke				
Stratification	-Modified CHAD ₂ DS ₂ VASC score strata (Low risk / Moderate risk/ High risk) - For stroke event type of stroke (ischemic or hemorrhagic)							

Type of analysis	Longitudinal	Cross-sectional	Longitudinal	Cross-sectional	Longitudinal	Longitudinal	Longitudinal	Longitudinal
Analysis methods	Descriptive	Descriptive	Cox regression model with OAC exposure considered as time-dependent variable (Crude and variable described in table XV)	Descriptive	Descriptive	Descriptive + ANOVA or Welch test or Kruskal-Wallis (according to the verification of the hypothesis) + post-hoc test (if previous global test significant)		Clustering models (TAK, K-Means, Random-Forest, Ascending hierarchical clustering) with a data visualization
Sensitivity analyses	
 -Integration of 2020 data -30 and 90 days of maximal number of days allowed for being refilled -Integration of all incident AF patients (i.e. inclusion of patients with an event of interest between inclusion date and index date) 	
 -Integration of 2020 data 	
 -Integration of 2020 data -30 and 90 days of maximal number of days allowed for being refilled 
 - Integration of all incident AF patients (i.e. inclusion of patients with an event of interest between inclusion date and index date) 	
 -Integration of 2020 data -Integration of all incident AF patients (i.e. inclusion of patients with an event of interest between inclusion date and index date) 
 - On AF patients identified only by LTD or hospitalization (new OAC users identified) 				

				by algorithm of Billionnet et al. not included)				
--	--	--	--	---	--	--	--	--

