- $N_{i,Y}$ represents the counts of patients at risk (French adult residents from census data in year Y minus count of prevalent diagnosed AF patients in year Y) in the age group i in the year Y

The estimations of the annual standardized incidence and annual prevalence of AF will be also performed according to exposure status (exposed to OAC or unexposed), every year. A patient will be considered exposed to OAC in a given year if the patient presents at least one sequence treatment for an OAC in the corresponding year.

9.7.4.4 Description of the use of oral anticoagulants (OACs) in AF incident patients initiating treatment (AF patients exposed to OAC therapy)

The analysis of the OAC treatment patterns will be descriptive and exploratory in nature.

The date of first reimbursement of any drugs of interest (VKA, apixaban, rivaroxaban, and dabigatran) will be considered as the regimen initiation date and mark the beginning of the identification of the treatment sequence (cf. table VII).

The duration of a prescription will be of 30 days for any drugs of interest. The grace period considered for any drugs of interest considered will be 60 days (30 days and 90 days will be considered for sensitivity analyses).

A treatment sequence will continue until one of the following occurs:

- A regimen switch, defined as the reimbursement of another OAC. The end date of the first treatment sequence is the day before the date of first reimbursement of another OAC.
- Discontinuation of drugs in the treatment sequence: if a period between two consecutive claims is superior to the duration of the treatment of the last claim, plus a permissible gap of at least 60 days (30 and 90 days for sensitivity analyses) then the medication is considered as stopped within the treatment sequence. The date of discontinuation (end date of the treatment sequence) will be fixed at the date of the last claim, plus the treatment duration of this last claim.
- End of follow-up.

The treatment pattern analysis will be providing the following information:

- Number and percentage of patients receiving each of OAC treatment during the follow-up
- Number and percentage of patients who received 1, 2, 3, 4 and 5+ sequence treatment during the follow-up
- Number and percentage of patients who have switched from an OAC to another during the follow-up

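### The SAP gives two populations for annual AF incidence (objective 4), and the one in the derivation table drops some true new cases that later received an OAC

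*SAP*

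**What the plan says.** **Sources that count all newly diagnosed AF**
- SAP 9.2.3.3.2 sets up two incident datasets. The first, for longitudinal objectives 1, 2, 3 and 7, requires new AF and no recent event. The second is described as "For cross-sectional analyses (objectives 2, 4, 5 and 6) and analysis for exploratory objective (objective 8") and requires only AF newly diagnosed in the inclusion period.
- SAP 9.7.4.3 puts incident diagnosed NVAF patients of year Y in the numerator and states no event exclusion. The SAP abstract (secondary objective 4) and the parameter table in Protocol Appendix 1 define incidence the same way.

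**Sources that apply, or imply, the event exclusion**
- SAP 9.4.3.3, Table XVI, defines Incident AF patient for this analysis only as "Binary variable (Yes / No) See Table X".
- SAP 9.4.2, Table X, makes that flag Yes only if AF is newly diagnosed and a second condition holds: "No reported events of interest (stroke, major bleeding, and death) between the inclusion date and the first date of OAC delivery". The second condition bears only on those who receive an OAC in the first 30 days. Everyone else is No.
- SAP Table XXI lists "Integration of all incident AF patients (i.e. inclusion of patients with an event of interest between inclusion date and index date") as a sensitivity analysis in the objective 4 column. The notes to shells A12 and A13 repeat it.

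**Sources that limit the re-inclusion analysis**
- SAP 9.7.6 item 1 and the note inside Table X restrict it to the rates of stroke, bleeding and death and their comparison. In 9.7.6, Tables A12 and A13 appear only under items 2 and 3 (2020 data, and omission of algorithm-identified patients).

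**Exposure for objective 4**
- SAP 9.7.4.3: "A patient will be considered exposed to OAC in a given year if the patient presents at least one sequence treatment for an OAC" in that year.

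**The concern.** An event-free condition makes sense for the follow-up analyses, where time starts at first dispensation and an earlier event would be misplaced. It has no role in counting new AF. A patient who had a stroke or bleed between inclusion and first OAC delivery is still a new case.

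The SAP derives only one incident flag, and it carries the condition. A programmer working from Table XVI and one working from 9.2.3.3.2 would therefore report different headline incidence rates. Because the condition applies only to patients dispensed an OAC within 30 days, the Table XVI route also shifts the exposed/unexposed split, which objective 4 is meant to supply. The patients lost are those with an early stroke or bleed.

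**Working it through.** The documents state no figure that can be reproduced here. The check is a comparison of the rules, followed by an illustration of scale.

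**1. Which patients the two rules treat differently**

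| Patient, all with newly diagnosed AF | 9.2.3.3.2 / 9.7.4.3 | Table XVI via Table X |
|---|---|---|
| No OAC within 30 days | incident | incident |
| OAC within 30 days, no event before delivery | incident | incident |
| OAC within 30 days, stroke or major bleed before delivery | incident | not incident |

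Only the last row differs, and there the Table XVI route can only lower the numerator. Death is listed in the condition but cannot operate, because a patient who died before first delivery has no dispensation. Under 9.2.1.2, a patient whose first evidence of AF is the OAC dispensation has inclusion and delivery on the same date. The loss therefore comes essentially from patients first identified by hospital stay or LTD.

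**2. Where the loss falls**

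The dropped patients all have a dispensation within 30 days, so they normally have an OAC sequence in the year of inclusion and belong to the exposed row. The exception is inclusion in one calendar year and first dispensation in the next. If the year is taken from the inclusion date and inclusions are spread evenly, that share is about gap/365: 15/365 = 4.1% for a 15-day gap and 30/365 = 8.2% for a 30-day gap.

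**3. Illustration of scale**

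Inputs: 225,747 new OAC users with AF in 2018 (SAP 9.5), and a standardized rate of 410 per 100,000 newly treated adults in 2018 (SAP 7.1). Let f be the share of OAC-treated new cases dropped. The documents give no value for f, so 0.5% to 10% is an assumption. The year-boundary exception is ignored.

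Patients lost per year = f × 225,747. Exposed rate observed = 410 × (1 − f).

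| f (assumed) | Lost per year | Rate per 100,000 |
|---|---|---|
| 0.5% | 1,129 | 407.95 |
| 1% | 2,257 | 405.9 |
| 2% | 4,515 | 401.8 |
| 5% | 11,287 | 389.5 |
| 10% | 22,575 | 369.0 |

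Overall incidence falls by f × s, where s is the exposed share of new AF. With s assumed at 70% to 90%, the fall is 0.7% to 0.9% at f = 1% and 3.5% to 4.5% at f = 5%.

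The exposed share itself is also pulled down. With a true share of 80%:
- f = 5%: 0.80 × 0.95 / (0.80 × 0.95 + 0.20) = 0.76/0.96 = 79.2%
- f = 10%: 0.72/0.92 = 78.3%

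**4. What f depends on**

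Inclusion for hospital-diagnosed AF is the start of the stay (9.2.1.2), and events count from any diagnosis position (Table VIII). Table VIII does not say which date a coded event takes within a stay. Table X does not say whether an event on the inclusion date falls inside the window. AF first coded during a stroke or bleeding admission could be dropped or kept on that choice alone.

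**The case against.** The strongest reply is that the objective 4 narrative is right and only the pointer is wrong. Where the event exclusion is intended, the analysis sections write it out (9.7.3.1, the second description in 9.7.4.1, and 9.7.4.2). It is absent from 9.7.4.3. Pointers in this SAP are unreliable: Table X sends Death to Table III, Table XV sends HAS-BLED to Table VI, and several references are broken. The A12 and A13 notes may be copied, since they also list 30- and 90-day grace periods that 9.7.6 item 4 ties to A2 and A10 only. Finally, if the restricted flag is used, the planned re-inclusion analysis would still show the unrestricted rate.

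Much of this stands, and it rules out several stronger readings:
- **That undercounting is a settled result.** The documents show a contradiction. The bias follows only if Table XVI is used.
- **That the loss is confined to the exposed group.** The year-boundary cases are an exception.
- **That the same patient without an OAC by day 30 stays in as unexposed.** A patient first dispensed on day 45 of the same calendar year is kept and counted as exposed under 9.7.4.3.
- **That every patient whose AF presents with a stroke is lost.** This depends on the unspecified event dating.
- **That the Protocol's background statement, "AF accounts for approximately 15% of all strokes", sizes the problem.** It gives the share of strokes due to AF, which is not the share of new AF that presents with stroke.

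The reply does not remove the point. The pointer does not stand alone, because Table XXI places the re-inclusion analysis under objective 4, which makes sense only if the main analysis excludes these patients. Nor is that sensitivity analysis a safe remedy: 9.7.6 does not list it for A12 or A13, and it would leave the estimate that meets 9.2.3.3.2 as the secondary one.

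**Conclusion.** The SAP is internally inconsistent on the objective 4 population, for both the main and the sensitivity analysis, and this should be settled before programming. Followed as written, Table XVI removes true new AF cases and biases overall and exposed incidence downward, with almost all of the loss in the exposed row. The direction is certain under that route.

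The size cannot be derived from the documents. The figures in the working rest on assumed values of f and of the exposed share and show scale only. A firm percentage undercount is not supported. The note under A13 suggests that the prevalence table may inherit the same restriction, so it needs the same correction.

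**What to change.** 1. Derive two flags: *Incident AF* (newly diagnosed in the inclusion period, nothing more) and *Incident AF, longitudinal set* (the same plus the no-event condition).
2. Point Table XVI, shells A12 and A13, and the other cross-sectional and exploratory analyses listed in 9.2.3.3.2 to the first flag. Keep the second for objectives 1, 3 and 7 and the longitudinal part of 2.
3. Remove the re-inclusion sensitivity analysis for objective 4 from Table XXI and from the A12 and A13 notes. It becomes redundant, and those places then agree with 9.7.6 item 1 and the Table X note.

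The cost is one extra derived variable and edits to a few tables and notes. No new data are needed, and the unrestricted count is already planned as a sensitivity analysis in Table XXI.

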9.4.3.5 Comparison of HCRU and associated costs

Table XVIII. Derived variables for HCRU and associated cost

Variable	Definition
HCRU	Categorical variable (hospital admission/hospital at home/palliative care/emergency visit/outpatient physician's visits (private practice, home or outpatient)/outpatient paramedic visits/ rehabilitation care facilities/dispensing of observable drugs (AF drugs and other) /medication related to AF/Lab tests/Medical procedures/Medical devices (LPP)/sickness benefits/reimbursed transports) Equal to: - "hospital admission" if the reimbursement corresponds to any hospital admission - "hospital at home" if the reimbursement corresponds to any home hospitalization stay - "palliative care" if the reimbursement corresponds to any palliative care stay - "emergency visit" if the reimbursement corresponds to any emergency visit - "outpatient physician's visits" if the reimbursement corresponds to any private practice, home or outpatient visit - "outpatient paramedic visit" if the reimbursement corresponds to any outpatient paramedic visit - "rehabilitation care facilities" if the reimbursement corresponds to any SSR stays - "dispensing of observable drugs" if the reimbursement corresponds to any observable drugs (AF drugs and other)

	
 - "medication related to AF" if the reimbursement corresponds to any anticoagulants, antiplatelets, antihypertensive drugs glucose-lowering drugs, lipid-lowering drugs, antiarrhythmics or beta-blockers - "Lab tests" if the reimbursement corresponds to any lab tests - "Medical procedures" if the reimbursement corresponds to any Medical procedures - "Medical devices (LPP)" if the reimbursement corresponds to any Medical devices (LPP) - "sickness benefits" if the reimbursement corresponds to any sickness benefits - "reimbursed transports" if the reimbursement corresponds to any reimbursed transports
Date of care	
Date variable
 
Equals to the value of date of care indicated in the data extraction and associated with the reimbursement

Cost	
Continuous variable (euros)
 
Equals to the value of cost (i.e. including reimbursed and non-reimbursed amounts) indicated in the data extraction and associated with the reimbursement

Number of occurrences	
Continuous variable
 
Equals to the number of occurrences where the two criteria are met:
 
 - The variable HCRU equals to the specified HCRU - The value of the variable Date of care falls in the specified time period
Rate of occurrences per patient-month	
Continuous variable (occurrence in month)
 
Equals to the value of the variable Number of occurrences divided by the duration of follow-up in month of the specified time period

Total cost HCRU	
Continuous variable (euros)
 
Equals to the sum of the values of the variable Cost where the two criteria are met:
 
 - The variable HCRU equals to the specified HCRU - The value of the variable Date of care falls in the specified time period

9.4.3.6 *Description of the therapeutic management before/after the first stroke occurring after initiation of OAC therapy*

Table XIX. Derived variables for the description of therapeutic management at 6 and 12 months before / after the first stroke occurring after initiation of AOC therapy

Variable	Definition
HCRU after first stroke	
Categorical variable (Ambulatory care/hospital care/rehabilitation care facilities/medications related to AF)
 
Equal to:
 
 - “Ambulatory care” if the reimbursement corresponds to any outpatient physician’s visits (private practice, home or outpatient) or outpatient paramedic visits or dispensing of observable drugs (AF drugs and other) - “Hospital care” if the reimbursement corresponds to any Hospital admission or Hospital at home or Palliative care or Emergency visit - “Rehabilitation care facilities” if the reimbursement corresponds to any SSR stays - “Medication related to AF” if the reimbursement corresponds to any anticoagulants, antiplatelets, antihypertensive drugs glucose-lowering drugs, lipid-lowering drugs, antiarrhythmics or beta-blockers
Date of care	
Date variable
 
Equals to the value of date of care indicated in the data extraction and associated with the reimbursement

Time period	
Categorical variable (“From 12 to 6 months before 1st stroke date”/ “From 6 months to the 1st stroke date” / “From 1st the stroke date to 6 months after” / “From 6 to 12 months after the 1st stroke date”)
 
Equals to “From 12 to 6 months before 1st stroke date” if date of care indicated in the data extraction and associated with the reimbursement is between 12 months and 6 months before 1st stroke
 
Equals to “From 6 months to the 1st stroke date” if date of care indicated in the data extraction and associated with the reimbursement is between 6 months and 1st stroke
 
Equals to “From 1st the stroke date to 6 months after” if date of care indicated in the data extraction and associated with the reimbursement is between 1st stroke and 6 months after 1st stroke
 
Equals to “From 6 to 12 months after the 1st stroke date” if date of care indicated in the data extraction and associated with the reimbursement is between 6 months and 12 months after 1st stroke

Number of occurrences	
Continuous variable
 
Equals to the number of occurrences where the two criteria are met:
 
 – The variable HCRU after first stroke equals to the specified HCRU after first stroke – The value of the variable Date of care falls in the specified time period
------------------------------	--

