6 SUPPLEMENTARY MATERIAL

Appendix 1 SNDS databases presentation and contents

Presentation of SNDS databases

The French health insurance information system (Système national d'information interrégimes de l'Assurance Maladie, SNIIRAM) was created in 1999 to track health care consumption and expenditures. It has been improved over time in terms of exhaustiveness and information availability. SNIIRAM has continued to grow and extend to become, in 2016, the cornerstone of the national health data system (Système National des Données de Santé, SNDS).

The SNDS now covers 98.8% of the French population, over 66 million persons, from birth or immigration to death or emigration. It contains individual data used for billing and reimbursement of outpatient health care consumption (DCIR database – inter-scheme consumption data) collected by the health insurance, private and public hospital data (PMSI database) and causes of death (National death registry, CépiDC) for some years. It will also gradually integrate social and medical data and data from complementary health insurance. Outpatient and hospital care data are collected from the social security card, treatment forms, private institution invoices and procedures and outpatient visits billed by hospitals.

DCIR database

Sociodemographic characteristics

Patient's gender, date of birth, eligibility for complementary universal healthcare insurance (CMUc), localization of residence, date of death (month and year), indicator of low income.

Reimbursed/medical data

- Long Term Disease (LTD) registration with start and end dates (costly chronic diseases, with ICD-10 codes). It is requested by the patient's practitioner and medically validated by the health insurance system. Once registered, patients receive full reimbursement for expenditures related to the LTD.
- Dates of professional healthcare visits (general practitioners, specialists, paramedics) and mode of exercise (private or public practice);
- Date and nature of realized lab tests (coded with the nomenclature code of the medical biology acts [NABM]), medical procedures (coded with CCAM) without medical indication nor results, dates of prescription and completion, total and reimbursed costs;

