OAC treatment patterns Line of treatment / regimen	Identified algorithmically using drug regimen, duration of treatment, and gaps between treatments. Number of lines of treatment (LOT), duration of treatment, time to next treatment will be estimated
Hospitalizations and length of hospitalizations per LOT	Identified with hospital diagnoses (primary, related, associated) and with the date of admission and date of exit from this hospitalization.
Clinical events of interest	Stroke (ischemic/ hemorrhagic) Major bleeding Death
Healthcare Resource use (HCRU) and costs	Ambulatory care Medical consultations and outpatient visits Medical and technical procedures, imaging, biologic tests Healthcare providers visits Hospital care (MCO) Hospitalizations, emergency room admissions Medical and technical procedures, imaging... Rehabilitation care facilities (SSR) Medications Including: Anticoagulants, antiplatelets, antihypertensive drugs glucose-lowering drugs, lipid-lowering drugs, antiarrhythmics, beta-blockers
Costs of HCRU	Health insurance perspective of direct costs of HCRU per resource used (ambulatory, hospital care, rehabilitation care...)

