9.3.1.2 Main data available

The data available in DCIR and PMSI databases that are of importance for this study are as follows:

- Administrative data used for sociodemographic, including:
 - o Date of birth (month and year);
 - o Date of death;
 - o Sex;
 - o City, department and region of residence;
 - o CMU-C;
 - o Aid for complementary health care (ACS) for elderly patients.
- Outpatient care data, including:
 - o Health professionals visited, medical specialty for physicians, dates of visits;
 - o Dates of dispensation, dates of reimbursement, type and number of services carried out by the health professional, reimbursed costs and costs paid by the patients for the associate cares;
 - o Drugs coded according to ATC and CIP classifications;
 - o Medical and technical acts coded according to CCAM;
 - o Biological acts coded according to NABM;
 - o Medical devices coded according to LPPR;
 - o Medical transportations;
 - o Sick leaves;
- Inpatient care data, including:
 - o Type of stay coded according to DRG;
 - o Localization, type and identifier of hospitals;
 - o Dates and reasons for admissions and discharges;
 - o Main, related and significant associated diagnoses of admissions coded according to ICD-10;
 - o Drugs dispensed at hospital and costly innovative drugs administered during admissions, both coded according to ATC and the common unit of dispensation (28nité commune de dispensation, UCD) classification;
 - o Medical and biological acts performed during admissions and coded according to CCAM and NABM, respectively;
 - o Other information such as stays in resuscitation units or intensive cares.
- Medical data, including:
 - o Presence of a LTD status, start and end dates of LTD coverage and nature of LTDs coded according to ICD-10.

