- Counts and percentages of patients with at least 1 reimbursement of specific OAC or no reimbursement for patients unexposed to OAC.
- Mean, SD, median, Q1, Q3, min and max of the rate of reimbursements per patient per month of follow-up in patients with at least 1 reimbursement of specific OAC or no reimbursement for patients unexposed to OAC.

All costs will be provided in Euros, annualized based on 2019 prices and presented per patients per month (PPPM) to consider differences in follow-up duration. Cost analysis will be performed from the health insurance perspective (reimbursed costs).

For the comparison of average of the overall PPPM costs (e.g. during all the follow-up) between AF incident patients exposed to apixaban, rivaroxaban, dabigatran vs NVAF patients exposed to VKA, significant differences between groups will be detected with an ANOVA for global equality of means. In case of the global test is significant, Tukey post-hoc test will be calculated to evaluate pair comparison. Normality will be tested before processing the analyses by the evaluation of the residuals (QQ plot and Shapiro-Wilk test) and homogeneity of variance with the Levene test and the plot of residuals versus fits. If normality not verified, Kruskal-Wallis test will be used. If homogeneity not verified, the Welch ANOVA will be used and Games-Howell for post-hoc test. The tests will be two-sided with a significance level of 5%.

9.7.4.6 Description of the therapeutic management before/after the first stroke occurring after initiation of OAC therapy

HCRU overall and for each resource (ambulatory care, hospital care, rehabilitation care facilities and medications) will be described at 6 and 12 months before and after the first stroke occurring after initiation of OAC therapy for patients exposed to apixaban, rivaroxaban, dabigatran and VKA in term of :

- Counts and percentages of patients with at least 1 reimbursement HCRU.

- Mean, SD, median, Q1, Q3, min and max of the rate of reimbursements per patient per month of follow-up in patients with at least 1 reimbursement of HCRU.

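### Table XVIII builds cost from reimbursed plus non-reimbursed amounts, although protocol and SAP declare a health insurance perspective with reimbursed costs

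*SAP*

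**What the plan says.** SAP Table XVIII (section 9.4.3.5) defines Cost in euros: "Equals to the value of cost (i.e. including reimbursed and non-reimbursed amounts". In the same table, Total cost HCRU is built directly from it: "Equals to the sum of the values of the variable Cost where the two criteria are met". The two criteria are the resource category and the time period; neither concerns who paid.

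SAP 9.7.4.5 states the perspective: "Cost analysis will be performed from the health insurance perspective (reimbursed costs". The same sentence stands in the SAP abstract under secondary objective 6 and in protocol 3.7.2.5. The study parameter table in protocol Appendix 1 agrees: "Health insurance perspective of direct costs of HCRU per resource used".

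On the data, SAP 9.3.1.2 lists among the outpatient items "reimbursed costs and costs paid by the patients for the associate cares". Protocol Appendix 1 lists total and reimbursed costs for laboratory tests and procedures, and for dispensed drugs and devices. On long-term disease (LTD) status, protocol Appendix 1 says: "Once registered, patients receive full reimbursement for expenditures related to the LTD".

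**The concern.** The definition and the declared perspective are two live instructions for the same analysis, and they give different numbers wherever care is not fully reimbursed. SAP 9.6 has the statistician create the derived variables as the signed-off plan instructs, so Table XVIII is what would be programmed. The second statistician's check of the programs would work from the same plan and need not catch the conflict.

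At stake are the per-patient-per-month costs in Table A15 and the tests in Table A16, where the DOACs and unexposed patients are set against VKA. Total cost HCRU also enters the exploratory clustering through Table XX. Protocol 2.4 foresees using the results in submissions to French health authorities, for whom it matters whether a euro figure is payer cost or total expenditure.

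**Working it through.** The plan states no cost figure, so there is nothing to reproduce. The check is a comparison of texts, followed by arithmetic for scale.

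**1. The texts side by side**

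| Place | Cost concept |
|---|---|
| SAP Table XVIII, Cost | reimbursed plus non-reimbursed |
| SAP Table XVIII, Total cost HCRU | sum of Cost, so the same |
| SAP abstract, objective 6 | reimbursed, health insurance perspective |
| SAP 9.7.4.5 | reimbursed, health insurance perspective |
| Protocol 3.7.2.5 | reimbursed, health insurance perspective |
| Protocol Appendix 1, parameter table | health insurance perspective, direct costs |

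**2. Does anything reconcile them?** I found nothing that does. No variable restricted to reimbursed amounts is derived, and 9.7.4.5 contains no step that strips out the rest. The shells of Tables A15 and A16 name no perspective. The SAP amendment table records no amendments, so the definition is not logged as a change.

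**3. Size of the overstatement.** Let T be total cost, P the payer's part and r = P/T. Reporting T as payer cost overstates it by T/P - 1 = 1/r - 1. The documents do not give r, so these values are assumptions:

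| Assumed r | 1/r - 1 |
|---|---|
| 1.00 | 0% |
| 0.90 | 11% |
| 0.80 | 25% |
| 0.70 | 43% |
| 0.65 | 54% |

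Here r is the share over all the care being summed. A value as low as 0.65 would have to hold across all of that care, not just one kind of service, for the 54% to apply to the total.

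**4. Comparison between groups.** For mean costs in groups A and B, T_A/T_B = (P_A/r_A)/(P_B/r_B) = (P_A/P_B) x (r_B/r_A).

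- If r_A = r_B = r, the ratio is unchanged, but each mean and each difference in euros is multiplied by 1/r.
- If the shares differ, the ratio is distorted by r_B/r_A. With assumed values r_A = 0.90 and r_B = 0.80, the factor is 0.80/0.90 = 0.89.

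The documents offer one route to unequal shares. LTD-related care is fully reimbursed, and entry to the cohort differs by exposure: under SAP 9.2.3.1 an OAC starter can enter through the prediction model without an AF hospital stay or AF LTD, whereas an unexposed patient needs one or the other. That makes unequal AF-LTD shares possible. It does not establish them or give their direction.

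**The case against.** The best defence is that 9.7.4.5 is the analysis section and governs, while Table XVIII only describes a raw field. This is weak: Total cost HCRU is built directly from Cost, and nothing comes between that variable and the tables.

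Three other objections stand, and each limits what can be claimed.

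- **Bias between groups.** A reader might infer that the exposure groups are inflated unequally and that the comparison is therefore biased. The documents give neither LTD shares nor reimbursed shares by group. SAP 9.3.1.1 adds that LTD registration may be missing because another chronic disease already covers the expenses, so having no AF LTD does not imply lower reimbursement. Full reimbursement also applies only to LTD-related care, so one patient can have both kinds.
- **Magnitude.** A reader might take 54% as an estimate. It rests on an assumed floor of 0.65 that appears nowhere in the documents.
- **Simplicity of the repair.** A reader might conclude that changing one line settles the matter. SAP 9.3.1.2 lists reimbursed amounts under outpatient care only. Its inpatient list names no cost item, and protocol Appendix 1 gives only a DRG-based cost coding system for hospital stays. Yet hospital stays are among the cost categories of Table XVIII.

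The documents also do not say who bears the non-reimbursed part beyond mentioning patients, so nothing should be concluded about other payers.

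**Conclusion.** The inconsistency is real and Table XVIII is wrong as written for the declared perspective. If followed, it yields total expenditure presented as payer cost throughout the cost results of secondary objective 6 (Tables A15 and A16), an overstatement wherever care is not fully reimbursed. This rests on the text alone.

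The size is 1/r - 1, with r unknown; 0% to 54% for r from 1.00 down to 0.65 is illustration only. Distortion of the comparison between groups is possible but conditional on reimbursed shares differing by exposure, which the documents do not show. The event-rate analyses, including the primary objective, do not use this variable. The test level is not in dispute.

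**What to change.** In Table XVIII, define Cost as the amount reimbursed by health insurance. Use the reimbursed amounts that the documents list for outpatient care, procedures, drugs and devices. For hospital stays, name the field or tariff that gives the payer amount. If total expenditure is of interest, derive it as a second variable with its own label and keep it out of tables presented as payer cost. State the perspective in the titles or footnotes of Tables A15 and A16.

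Rewording the perspective instead would also restore consistency, but it would mean editing both protocol and SAP and giving up the perspective that both declare.

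The cost is small: one definition, one added specification for the valuation of hospital stays, and table labels. The documents point to no new data for the outpatient part. Whether the extraction holds a payer amount for hospital stays has to be confirmed before programming.
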